Clinical Research	Professional Education and Research Institute
Organization	[name]
	[contact]
	Email [contact]
	 

Confidential Page 7 of 73

TABLE 2: VERSION HISTORY

Version Number	Release Date	Change(s)	Reason for Change
1.0	08AUG2023		Initial Release
		Revised language to Exclusion Criteria #10 to a 30% heal rate from SV1- TV1.	Change to Inclusion/Exclusion Criteria
2.0	04MAY2023	Addition of Randomization Review Panel between SV2 and TV1	Change to Randomization Process
		Updated number of sites and other minor administrative changes were also added.	Administrative Change

Confidential Page 8 of 73

LIST OF ABBREVIATIONS

TERM	DEFINITION
ABI/ABPI	Ankle/Brachial Index/Ankle Brachial Pressure Index
AE	Adverse Event
CFR	Code of Federal Regulations
CRF	Case Report Form
DFU	Diabetic foot ulcer
EOS	End of study
FDA	Food and Drug Administration
GCP	Good Clinical Practice
HCV	Healing Confirmation Visit
HIPAA	Health Insurance Portability and Accountability Act
HIV	Human Immunodeficiency virus
IRB	Institutional Review Board
ITT	Intent-to-treat
PAR	Percentage area reduction
RCT	Randomized controlled trial
SAE	Serious adverse event
SAP	Statistical analysis plan
SOC	Standard of care
SOP	Standard operating procedure
SPP	Skin perfusion pressure
SV	Screening visit
TCOM	Transcutaneous oxygen measurement
TV	Treatment Visit
US	United States of America
WOUND-Q	Wound quality scale

Confidential Page 9 of 73

PROTOCOL SYNOPSIS: ETS-MG-DFU-02

Objective	The purpose of this clinical evaluation is to collect patient outcome data on a commercially available 510K FDA cleared synthetic, absorbable skin substitute matrix. The commercially available product is MIRRAGEN™ Advanced Wound Matrix and consists of a borate-based bioactive glass fiber and particulate. In this trial, two groups of diabetic foot ulcers (DFUs), will receive standard of care (SOC) treatment for their condition. Half of the patients will have their SOC treatment with a 510K FDA cleared Collagen alginate dressing FIBRACOL™ and the other half will have a 510K FDA cleared MIRRAGEN™ Advanced Wound Matrix as the primary treatment. The primary endpoint is the percentage of patients that go on to complete closure of the target ulcer between the two groups: SOC with FIBRACOL™ or SOC with MIRRAGEN™. Secondary endpoints include the proportion of subjects achieving complete
Intervention	wound closure of the target ulcer by end of 12 weeks.
Intervention Groups	Group 1: SOC primary dressing with MIRRAGEN™
3.00Pe	Group 2: SOC primary dressing with FIBRACOL™
Study Design	Multi-center, open label, randomized controlled trial
Sample Size	For this RCT, N = up to 240 subjects
Centers	Up to 15 centers within the United States, Open/competitive enrollment.
Endpoints	Primary endpoint: - The proportion of subjects that obtain complete closure over the 12-week treatment period Secondary endpoints: - The time to achieve complete wound closure of the target ulcer by the end of 12 weeks
	 Percentage wound area reduction from TV1 to TV13 measured weekly with digital photographic planimetry and physical examination
	The number and type of Treatment Emergent Adverse and Serious Adverse Events
	 Change in peripheral neuropathy of the target foot assessed using the standard 10-point Semmes-Weinstein monofilament exam [Time Frame: TV1, TV3, TV7, TV9, and EOS1]
	 Change in pain in the target ulcer assessed using the NPRS scale. [Time Frame: TV1, TV3, TV7, TV9, and EOS1]

Confidential Page 10 of 73

Version 2.0 Date: May 12, 2023 Change in quality of life using WOUND-Q assessment [Time Frame: SV1, TV3, TV7, EOS1] **Exploratory Endpoint:** Difference in cellulitis and/or infection at 12 weeks Use of near-infrared tissue oxygenation imaging assessment of wounds at select sites to evaluate changes in vascularization/oxygenation of wounds with treatment (Kent Imaging SnapshotNIR: Time Frame: SV1, TV1 pre-randomization, TV2, TV4, TV7, and EOS1. Safety There is no formal safety objective for this study as MIRRAGEN™ and FIBRACOL™ are commercially available, 510K FDA cleared dressings for diabetic foot wounds. Therefore, in accordance with FDA regulations, adverse reactions to the dressings will be recorded and provided to the study Sponsor for required FDA reporting and will be concurrently reported to all Investigators and IRBs. Adverse events associated with application of standard of care dressing will be collected during the course of the study. Collection and reporting of any adverse reaction data, in accordance with FDA regulations and adverse events associated with dressing application will ensure study subject safety.

Surveillance Schedule

Following initial enrollment, subjects will undergo a screening phase, consisting of 14 days, to determine eligibility. Eligible subjects will then undergo up to a 12-week treatment phase involving weekly evaluations and after 12 weeks, will exit the study. Additionally subjects in either group whose ulcers have not reduced by 50% at week 7 of treatment will be considered a treatment failure and will be exited from the study and permitted to seek alternative treatment.

Study Duration

It is estimated that about 15 months will be required to complete the study with data collection and reporting.

Confidential Page 11 of 73

Inclusion Criteria

Potential subjects are required to meet all the following criteria for enrollment into the study and subsequent randomization.

- 1. Subjects must be at least 18 years of age or older.
- 2. Subjects must have a diagnosis of type 1 or 2 Diabetes mellitus.
- 3. At randomization subjects must have a target diabetic foot ulcer with a minimum surface area of 1.0 cm² and a maximum surface area of 20.0 cm² measured post debridement with a photographic planimetry app.
- 4. The target ulcer must have been present for a minimum of 4 weeks and a maximum of 52 weeks of standard of care prior to the initial screening visit.
- 5. The target ulcer must be located on the foot with at least 50% of the ulcer below the malleolus.
- 6. The target ulcer must be full thickness on the foot or ankle that does not probe to bone.
- 7. Adequate circulation to the affected foot as documented by any of the following methods performed within 3 months of the first screening visit:
 - a. TCOM ≥30 mmHg
 - b. ABI between 0.7 and 1.3
 - c. PVR: Biphasic
 - d. TBI >0.6
 - e. As an alternative arterial Doppler ultrasound can be performed evaluating for biphasic dorsalis pedis and posterior tibial vessels at the level of the ankle
- 8. If the subject has two or more ulcers, they must be separated by at least 2 cm. The largest ulcer satisfying the inclusion and exclusion criteria will be designated as the target ulcer.
- 9. Target ulcers located on the plantar aspect of the foot must be offloaded for at least 14 days prior to randomization.
- 10. The subject must consent to using the prescribed off-loading method for the duration of the study.
- 11. The subject must agree to attend the weekly study visits required by the protocol.
- 12. The subject must be willing and able to participate in the informed consent process.

Confidential Page 12 of 73

Exclusion Criteria

Exclusion Criteria:

Potential subjects meeting any of the following criteria will be excluded from enrollment and subsequent randomization.

- 1. A subject known to have a life expectancy of < 6 months is excluded.
- 2. If the target ulcer is infected or if there is cellulitis in the surrounding skin, the subject is excluded.
- 3. Presence of osteomyelitis or exposed bone, probes to bone or joint capsule on investigator's exam or radiographic evidence.
- 4. A potential subject cannot have an infection in the target ulcer or in a remote location that requires systemic antibiotic therapy.
- A subject receiving immunosuppressants (including systemic corticosteroids at doses greater than 10 mg of Prednisone per day or equivalent) or cytotoxic chemotherapy is excluded.
- 6. The topical application of steroids to the ulcer surface within one month of initial screening is not permitted.
- A subject with a previous partial amputation on the affected foot is excluded if the resulting deformity impedes proper offloading of the target ulcer.
- 8. If a subject has a glycated hemoglobin (HbA1c) greater than or equal to 12% taken at or within 3 months of the initial screening visit he/she is excluded.
- 9. If a subject has a serum creatinine ≥ 3.0mg/dL within 6 months of randomization he/she is excluded.
- 10. The subject is excluded if the surface area measurement of the target ulcer has reduced in size by more than 30% in the 2 weeks prior to the initial screening during the 2-week screening phase: the 2 weeks from the initial screening visit (SV1) to the TV1/randomization visit during which time the subject received SOC.
- 11. A subject with an acute Charcot foot, or an inactive Charcot foot, that impedes proper offloading of the target ulcer is excluded.
- 12. Women who are pregnant or considering becoming pregnant within the next 6 months are excluded.
- 13. A potential subject with end stage renal disease requiring dialysis is excluded.
- 14. A subject who participated in a clinical trial involving treatment with an investigational product within the previous 30 days is excluded.
- 15. A subject who, in the opinion of the Investigator, has a medical or psychological condition that may interfere with study assessments is excluded.

Confidential Page 13 of 73

Version 2.0	Date: May 12, 2023
	1C. A public of two story with humanharia average the ways or a Callular and/or
	16. A subject treated with hyperbaric oxygen therapy or a Cellular and/or
	Tissue Product (CTP) in the 30 days prior to the initial screening visit
	is excluded.

1 INTRODUCTION

1.1 Costs of Non-healing Diabetic Foot Ulcers

The economic burden of DFUs costs the United States over \$50 billion each year.¹ The cost to treat one patient with DFUs ranges from \$11,700 to \$16,883.² Although approximately 70% of DFUs are shown to heal with good SOC, at least 30% become chronic wounds.³ These non-healing wounds are at greater risk for infection and lower extremity amputation.⁴ Consequently, good standard of care therapy is important for patients with chronic DFUs to improve patient outcomes, lower treatment costs and reduce the risk of complications.

1.2 MIRRAGEN™ Advanced Wound Matrix

MIRRAGEN™ Advanced Wound Matrix is intended for the use in the management of wounds. Wound types include: partial and full thickness wounds, pressure ulcers, venous ulcers, diabetic ulcers, chronic vascular ulcers, tunneled/undermined wounds, surgical wounds, trauma wounds and draining wounds.

Boron-containing compounds have an extensive history of use in medicine due to several mechanisms of action, including inhibition of phodsphodiesterase-4 (PDE4), which reduces production of pro-inflammatory cytokines⁴; broad-spectrum antifungal activity (inhibitor of amino-acyl (leucyl) *t*RNA synthetase)⁵; treatment of various cancers (e.g., non-Hodgkin's lymphoma and multiple myeloma)^{6,7}; antimicrobial activity against Gram-negative bacteria (AN3365)⁸; and antiprotozoal activity against Trypanosoma brucei.⁹

Although borate itself was shown to accelerate wound healing in wounds nearly 30 years ago^{10,} it has taken some time to understand the mechanisms involved. Boron facilitates the activity of several key enzymes in fibroblasts, including elastase, trypsin-like enzymes, collagenase, and alkaline phosphatase.¹¹ Further research showed that it also regulates mRNA expression of a wide range of extracellular-matrix proteins, including collagen type 1 (COL1), osteopontin (OPN), bone sialoprotein (BSP), and osteocalcin (OCN), as well as alkaline phosphatase and bone morphogenetic proteins (BMPs).^{12,13}

In vitro studies of bioactive boron-based glass fiber matrices have been conducted for several years, primarily in bone and cartilage although two in-vitro studies suggest that boron-doped bioactive glass fibers are capable of eliciting VEGF responses from cells^{14,15} although no studies to date have confirmed such responses in chronic wounds. In general, it has been found that the degradation rate of bioactive glass can be altered by changing its composition; for example, by partially replacing the SiO₂ in silicate 45S5 or 13–93 glass with B_2O_3 (yielding a borosilicate bioactive glass), or fully replacing the SiO₂ with B_2O_3 (producing a borate bioactive glass)^{16,17}.

Recent clinical studies have pointed to the efficacy of boron-based bioactive glass fiber matrix in wound management¹⁸⁻²¹. This RCT is a larger, follow-up study to the recently

Confidential Page 14 of 73

published 40-patient pilot study in DFU which demonstrated a statistically significant 2.8 fold increase in healing rates compared to SOC alone (p=0,004) and doubled the rate of wound are reduction at all time points $(p-0.027)^{22}$.

Confidential Page 15 of 73

2 Rationale for Study

MIRRAGEN™ is a bioactive borate-based glass fiber matrix (BBGFM) that can dissolve in wound fluids over a period of several days. A recent 40-patient RCT and additional case studies involving the treatment of chronic diabetic foot ulcers (DFUs) with BBGFM suggest that when used as dressing as part of the standard of care (SOC), improved healing trajectories result. Based on this early promising data, a larger RCT is necessary to further validate these results. For consistency one type of wound will be studied in this trial and we have chosen DFU's as they are some of the most common wounds seen in the wound clinics.

Confidential Page 16 of 73

3 Study Endpoints

The purpose of this clinical evaluation is to collect patient outcome data on 2 commercially available standard of care dressings in partial/full-thickness diabetic foot ulcer subjects. Patient outcomes will be compared at 6 and 12 weeks.

The **primary endpoint** is the proportion of subjects that obtain complete closure over the 12-week treatment period.

Secondary endpoints include a comparison between groups of the following clinical measures:

- 1. The time to achieve complete wound closure of the target ulcer by the end of 12 weeks.
- 2. Percentage wound area reduction from TV1 to TV13 measured weekly with digital photographic planimetry and physical examination.
- 3. The number and type of Treatment Emergent Adverse Events.
- 4. Change in peripheral neuropathy of the target foot assessed using the standard 10-point Semmes-Weinstein monofilament exam [Time Frame: TV1, TV3, TV7, TV9, and EOS1].
- 5. Change in pain in the target ulcer assessed using the NPRS scale. [Time Frame: TV1, TV3, TV7, TV9, and EOS1].
- 6. Change in quality of life using WOUND-Q assessment.

Exploratory/Tertiary Endpoints

- 7. Difference in cellulitis and/or infection at 12 weeks.
- 8. Use of near-infrared tissue oxygenation imaging assessment of wounds at select sites to evaluate changes in vascularization/oxygenation of wounds with treatment (Kent Imaging SnapshotNIR; Time Frame: SV1, TV1 pre-randomization, TV2, TV4, TV7, and EOS1).

Confidential Page 17 of 73

4 Study Design

This study is a prospective, multi-center, open label, RCT designed to collect patient outcome data on two commercially available SOC dressings for the treatment of DFUs. Wound healing assessment will be conducted by a clinician, other than the Investigator at each site. Confirmation of wound healing will be overseen by an independent adjudication committee made up of wound care experts.

There are two standard of care arms in the study:

Arm 1: The SOC therapy in this study is offloading of the DFU (CAM boots or total contact casting [TCC] if the subject's foot is too large for a CAM), appropriate sharp or surgical debridement, infection management (systemic antibiotics only in conjunction with debridement) and wound care covering with Bioactive glass dressing, MIRRAGEN™, followed by a padded 3-layer dressing comprised of 4x4 gauze pads, soft roll and compressive wrap (Dynaflex™ or equivalent).

Arm 2: The SOC therapy in this study is offloading of the DFU (CAM boots or total contact casting [TCC] if the subject's foot is too large for a CAM), appropriate sharp or surgical debridement, infection management (systemic antibiotics only in conjunction with debridement) and wound care covering with calcium alginate FIBRACOL™ dressing followed by a padded 3-layer dressing comprised of 4x4 gauze pads, soft roll and compressive wrap (Dynaflex™ or equivalent).

The study involves two phases: Screening and Treatment.

FIGURE 2: OVERVIEW OF STUDY PHASES

4.1 Phase 1: Screening

The Screening Phase (14 days required) is designed to determine whether subjects are eligible to proceed to the Treatment Phase of the study and consists of a series of screening assessments designed to determine eligibility.

At the first Screening Phase Visit (SV1), written informed consent (ICF) from the subject will be obtained by the Investigator or suitably qualified designee before any protected health information is obtained and prior to the performance of any protocol-specific procedures.

After obtaining ICF, the Investigator will select the study index ulcer. Each subject will have only one DFU selected as the index ulcer. If the subject has more than one DFU at the SV 1 visit, the Investigator will select the largest DFU that meets the eligibility criteria of the protocol as the index ulcer.

Subjects whose index ulcer has been treated with SOC for two weeks during screening are eligible to enter the Treatment Phase immediately once all of the inclusion and exclusion criteria are met. Further, a panel of three board-certified plastic surgeons will review each wound, as well as inclusion/exclusion criteria, in a blinded fashion to ensure that randomizations are appropriate. The review will occur between SV2 and the day of randomization. The plastic surgeon will provide correspondence to the trial manager that the subject is appropriate for randomization, prior to the site being able to randomize the patient.

Confidential Page 18 of 73

4.2 Phase 2: Treatment

The Treatment Phase (up to 13 weeks) begins with a series of assessments designed to confirm the subject's continued eligibility. Investigators will debride the ulcer, in accordance with SOC if required. Subjects whose ulcers continue to meet eligibility criteria will then be randomized to one of two groups: (1) SOC with MIRRAGEN™ primary dressing or (2) SOC with FIBRACOL™ primary dressing. Additionally for the most compassionate care subjects in either group whose ulcers have demonstrated wound area reduction by less than 50% at week 7 of treatment will be considered a treatment failure and will be permitted to obtain additional outside treatment and thus will be exited from the study.

4.3 Subject Treatment Assessments

4.3.1 DFU Assessments

During the Treatment Phase, subjects will be evaluated on a weekly basis. Weekly patient outcome evaluations include the Investigator's assessment of ulcer healing and measurements of ulcer size using digital imaging to measure wound area and provide photos of wounds, including photos of healed wounds for adjudication.

Note: All procedures required during baseline are included in TV1 prior to the Randomization visit.

Other evaluations during the Treatment Phase are detailed in the procedures section.

Subjects will be seen weekly (± 3 days) until the ulcer is healed or they meet protocol criteria to exit the study.

4.3.2 Wound Healing Assessment

Initial and confirmation evaluations of wound healing will be subject to oversight to reduce bias. An adjudication panel, consisting of at least two wound care experts with significant experience in treating diabetic foot ulcers will be employed.

The adjudication will be made using photographs of the DFU and will comprise:

- 1. An initial wound healing assessment by an Investigator.
- 2. The subject proceeds to the wound healing confirmation visit, two weeks later.
- Subject photographs will be cataloged and presented to the adjudicators during an
 adjudication meeting held at interim points throughout the study (up to two interim
 adjudication meetings) and at the end of the study (up to three total adjudication
 meetings).
- 4. Final healing confirmation will be determined by the adjudicator during an adjudication meeting.

Confidential Page 19 of 73

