5.2 Success and Failure

- A subject whose ulcer heals by 13 weeks and has been confirmed as healed two weeks later will be considered a treatment success
- A subject whose ulcer has failed to heal by 50% or greater at TV7 or six weeks after randomization will be considered a treatment failure
- A subject whose ulcer has failed to heal by 13 weeks will be considered a treatment failure
- A subject who is withdrawn from the trial and/or experiences an amputation is also considered a treatment failure

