9.1 Data Analysis

This study consists of primary, secondary and exploratory/tertiary (research) endpoints. Data analysis of study endpoints includes use of validated DFU wound healing measures, quantitative and qualitative analyses, as well as exploratory methodologies. Table 4 below details each study endpoint, corresponding data, and planned analyses.

TABLE 4: ETS WOUND CARE, LLC DFU ENDPOINT DATA ANALYSIS

Endpoint	Endpoint Description	Supporting Study Data	Endpoint Analysis
Primary	Comparison of the proportion of index ulcers "healed" at 12 weeks	Investigator assessment of healing (100% epithelization w/no drainage), measurements of ulcer size using digital imaging and photos	Adjudication panel will determine using photographs of the DFU
	Proportion of Index Ulcers healed at 6 weeks		
	PAR at 6 and 12 weeks	Digital imaging	Mathematical wound area change
	Time to healing within 6 and 12 weeks	Primary endpoint	Mathematical time based on healing
Secondary	Changes in peripheral neuropathy	Semmes Weinstein with vibratory	Mathematical change in scores
	Changes in wound quality of life	WOUND-Q (Quality of life tool)	Mathematical change in scores
	Change in pain levels during trial	NPRS	Mathematical change in scores
	Difference in cellulitis and/or infection at 12 weeks	Observation	Count of positive and negative responses
Exploratory/Tertiary	Changes in tissue perfusion of wound bed and periphery with treatment	SnapshotNIR	Exploratory

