9.2 Statistical Analysis

Descriptive statistical methods will be used to summarize the data from this study with hypothesis testing performed for the primary and other selected efficacy endpoints. All testing for endpoints will be two-sided with alpha set at .05 level of significance if no statistical testing is done at the interim analysis at 0.044 if statistical testing is done at N=240.

A formal Statistical Analysis Plan (SAP) will be created prior to database lock. The primary endpoint analysis will be at 12 weeks and a series of secondary and exploratory/tertiary

Confidential Page 49 of 73

endpoints will be analyzed at 6 and 12 weeks. The SAP will provide a more technical and detailed description of the proposed data analysis methods and procedures. Any deviation from the analyses outlined in the protocol will be described in the most current version of the SAP. All statistical analyses will be conducted using PASW 28.

The primary study hypothesis is that the proportion of wounds healed at 12 weeks, after up to 12 weeks of SOC with MIRRAGEN™ and SOC with FIBRACOL™, will be equal for Groups 1 and 2. Formally, H0: I1–I2 = 0; HA: I1–I2 = D1≠0, where I1 is the proportion of wounds healed in Group 1, I2 is same metric for Group 2, D1 is the difference (I1–I2); assuming the alternative hypothesis and statistical test used is chi square/Fisher exact test. Analysis may be adjusted using generalized linear modeling based on available variables at baseline known to affect wound healing.

Group sequential trials with sample sizes of 120 and 120 at the final look achieve 100% power to detect a difference of 0.35 between group 1 (the MIRRAGEN™ group) (proportion 0.70) the control group (SOC with FIBRACOL™) proportion of 0.35 at the 0.049 significance level (alpha) using a two-sided Z-Test (Pooled).

The populations defined for analysis will include the intent-to-treat (ITT) and per protocol (PP). Additional analysis populations may be defined to evaluate study results. Any additional analysis populations will be defined in the SAP.

Envelopes will be created with a random allocation sequence, which will be composed of a random sequence of block sizes of 10 designed to achieve a balanced design.

One interim analysis will be performed (N~100). The object of the interim analysis is to assess subject outcomes between the groups, in particular to assess any adverse effects or events, such as infection and to recalculate sample size for the primary endpoint.

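### As written, adjudication starts from a site healing call, and no step has the panel read an ulcer that the site judged not healed

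*Combined protocol and SAP*

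**What the plan says.** The study is open label (synopsis; section 4).

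Section 4.3.2 says oversight of healing evaluations is there to reduce bias. It lists four steps: "An initial wound healing assessment by an Investigator"; a confirmation visit two weeks later; presentation of subject photographs at adjudication meetings (up to three in all); and final confirmation of healing by the adjudicator. Section 4.3.1 describes weekly imaging, "including photos of healed wounds for adjudication". Sections 4.5.3.3, 4.5.4 and 8.10.4 schedule the confirmation visit only after the site has judged the ulcer healed.

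For the primary endpoint, Table 4 in section 9.1 gives the analysis as "Adjudication panel will determine using photographs of the DFU" and does not say which ulcers are meant.

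Failure is defined in section 5.2. It covers "A subject whose ulcer has failed to heal by 50% or greater at TV7 or six weeks after randomization", an ulcer not healed by 13 weeks, and any subject withdrawn or with an amputation.

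The protocol is inconsistent on who makes the first call. Section 4 gives it to a clinician other than the Investigator; sections 4.3.1, 4.3.2, 4.5.3.3, 4.5.4 and 8.10.4 give it to the Investigator. Neither is said to be masked. The word blinded is used only for the eligibility panel that meets before randomization (sections 4.1, 4.5.2 and 8.2).

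**The concern.** Adjudication in an open-label trial should protect against site calls that lean either way. The described sequence protects against one direction. A closure called too readily reaches the panel and can be rejected. A closure that the site does not call triggers no confirmation visit and enters none of the four steps, so it counts as a failure on the site's word.

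If site staff who know the arm are slower to declare closure on the comparator dressing, and some of those closures are never called by the final visit, the comparator's rate falls and the difference widens in favour of the sponsor's product. Nothing in the plan would show that this had happened. Most of the unreviewed outcomes would also lie in the comparator arm, because more failures are expected there.

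**Working it through.** **Inputs.** From section 9.2: 120 per arm, planned closure 0.70 (MIRRAGEN) and 0.35 (control), two-sided pooled Z-test at 0.049. The rates of missed calls and the 50% common closure rate in step 3 are assumptions; the documents give neither.

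**1. The plan's own figure.** The protocol states "Group sequential trials with sample sizes of 120 and 120 at the final look achieve 100% power". With a critical value of 1.969 and a pooled proportion of (0.70 + 0.35)/2 = 0.525:
- SE under the null = √(0.525 × 0.475 × 2/120) = 0.0645
- SE under the alternative = √(0.70 × 0.30/120 + 0.35 × 0.65/120) = 0.0604
- Power = Φ[(0.35 − 1.969 × 0.0645)/0.0604] = Φ(3.69) = 0.9999

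This rounds to the stated 100%, so the inputs are read correctly. It is a single-look approximation; the group-sequential boundary is not given.

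**2. Outcomes outside the described review.**

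| Arm | Planned closures | Planned failures |
|---|---|---|
| MIRRAGEN | 120 × 0.70 = 84 | 36 (30%) |
| Control | 120 × 0.35 = 42 | 78 (65%) |
| Total | 126 (52.5%) | 114 (47.5%) |

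The total share would be 65% if both arms closed at 0.35, and 30% if both closed at 0.70.

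The 114 is an upper figure for what panel review could alter, for two reasons. Some are failures by rule (withdrawal, amputation, under 50% reduction at TV7), where reading for closure may change nothing. Some may be ulcers that the site called closed and the panel rejected, which did reach the panel. The documents give no number for either.

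**3. Illustration with no true difference.** Let true closure be p in both arms, and let a fraction m of control closures never be called. The recorded control rate is then p(1 − m). The false-positive rate is the sum, over all pairs of counts, of Bin(120, p) × Bin(120, p(1 − m)) where |Z| > 1.969.

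| m | Recorded control rate at p = 0.50 | False-positive rate at p = 0.50 | At p = 0.35 |
|---|---|---|---|
| 0 | 0.500 | 0.045 | 0.050 |
| 5% | 0.475 | 0.062 | 0.059 |
| 10% | 0.450 | 0.112 | 0.088 |
| 15% | 0.425 | 0.202 | 0.138 |

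**4. If the planned effect is real.** Start from 84 v 42 closures and move k control failures to closure:
- k = 27: 84 v 69, Z = 0.1250/0.0621 = 2.01, still significant
- k = 28: 84 v 70, Z = 0.1167/0.0619 = 1.88, no longer significant

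So 28 of the 78 control failures would have to be reversed.

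**The case against.** Four objections carry weight.

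**The text does not restrict the panel.** A reader might infer that the panel sees only called closures and can never see a failure. The protocol does not say so. Section 4.3.2 speaks of subject photographs without limit, Table 4 can be read as covering every ulcer, and section 4.3.1 mentions healed-wound photographs as part of a wider set. This stands: the restriction is inferred from the order of the steps. What remains is that no step for reading unhealed ulcers is described. If Table 4 means all ulcers, section 4.3.2 still has to say how.

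**The first caller may not be the Investigator.** Section 4 names another clinician. The passages conflict and must be reconciled. Because that clinician is not said to be masked either, the concern is reduced only if masking is added.

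**This overlaps with assessor masking.** The harm needs a first caller who knows the arm, so an effectively masked site assessor would remove most of it. That is correct, and the point should not be presented as independent of masking. Masking the panel alone would not help, because it would still have no route to an uncalled closure.

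**The size can be overstated.** A reader might take 47.5% as the share of outcomes at risk. It is not, for the two reasons given with the table of failures. A closure called late but still by the final visit also leaves the primary endpoint unchanged and affects only time to closure.

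**Conclusion.** The point holds in this form: adjudication as described is triggered by a site healing call, and no step lets the panel find or restore a closure that the site did not call. In an open-label trial with no stated masking of the site assessor, the described check works in one direction.

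Up to 47.5% of primary outcomes lie outside it at the planning rates. The documents do not support saying that half of the outcomes are at risk, or that the protocol bars the panel from seeing failures.

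The danger is greatest when the true effect is null or modest. Under the assumed 50% closure in both arms, 5% of control closures uncalled adds less than 0.02 to the error rate, and 15% raises it to about 0.20. If the planned effect is real, under-calling is unlikely to overturn the result. Whether sites would under-call in one arm at all cannot be known from the documents. The change is advisable, not essential to the trial's validity.

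**What to change.** In section 4.3.2, state that the existing panel, at its planned meetings, reads photographs from every randomized subject:
- for called closures, the closure and confirmation visits;
- for the rest, the last weekly visits, or TV7/EOS1 for early exits.

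Present them in random order with arm, site and the site's call hidden. Report disagreement between site and panel by arm, and repeat the primary test on the panel's calls as a sensitivity analysis. Align section 4.3.1 and Table 4 with this. Reconcile section 4 with the sections that name the Investigator as first assessor, and state whether that assessor is masked.

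State the limits in the same place:
- Section 8.10.4 requires absent drainage, which photographs may not show.
- A closure first visible at the last visit without a site call has no later photograph, so it cannot be confirmed at two weeks.
- The reading does not re-check the TV7 area measurement.

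**Cost.** An edit to the protocol and to any adjudication charter, and about 114 more photograph sets for the same panel to read. No new visits or images are needed, because the schedule of visits already has the index ulcer photographed at every visit.
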